Aim 2: Refine and test *NuestraSaludSegura* to determine its impact on COVID-19 testing and vaccination among Spanish-speaking Latinx persons using a group-randomized trial design.

Integrating our successes with peer navigation and mHealth strategies with other relevant COVID-19 studies and Aim 1 findings, we will refine and test the *NuestraSaludSegura* intervention. We will enroll 20 peer navigators, known as *Navegantes*, who represent 20 unique social networks, and 8 unique members from each social network for a total of n=160 social network members. After baseline data collection, we will randomize *Navegantes*, coupled with their social networks, into intervention and delayed-intervention groups (10 *Navegantes*; 80 social network members per group). We will train and support intervention-group *Navegantes* to increase COVID-19 testing and vaccination services within their social networks. We will evaluate the intervention by comparing changes in testing and vaccination from baseline to post-intervention follow-up between groups. *We hypothesize that intervention group will demonstrate increased COVID-19 testing and vaccination*.

Aim 3: Develop and disseminate practice, research, intervention, and policy priorities and recommendations to increase COVID-19 testing and vaccination among Spanish-speaking Latinx communities in the US. We will conduct an empowerment theory-based forum with Latinx community members and other community members and representatives from community-based organizations and universities to develop and disseminate priorities and recommendations based on study findings.

Methods and Measures

Design

Aim 1:

We will conduct **individual in-depth interviews** with two categories of participants from across NC: (1) Health providers (including administrators, clinicians, community health workers, and safety-net clinic staff), who have planned, managed, and/or conducted COVID-19 testing and/or vaccination activities for Spanish-speaking communities; and (2) Representatives from Latinx-serving community-based organizations. We also will conduct **focus groups** with Spanish-speaking Latinx community participants.

Aim 2:

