We will refine and test the *NuestraSaludSegura* intervention, integrating our previous successes with peer navigation and mHealth strategies with other relevant COVID-19 studies and Aim 1 findings. We will then recruit, enroll, and collect baseline data from 20 *Navegantes* (peer navigators) and their social network members (n=8 unique social network members per *Navegante*) from across NC. *Navegantes* (coupled with their social networks) will be randomly assigned to: intervention or delayed-intervention groups (10 *Navegantes*; 80 social network members per group). Intervention-group *Navegantes* will be trained and supported for 6 months of implementation in Years 1-2; delayed-intervention group *Navegantes* will be trained in Year 2. CBPR partners emphasized that a delayed-intervention comparison design is the most equitable, acceptable, and ethical.

Assessment of intervention efficacy. We will use a longitudinal group-randomized trial design with 2 arms (intervention and delayed-intervention) to evaluate the impact of the intervention. Quantitative outcome data will be collected from each *Navegante* and their 8 enrolled social network members at 2 time points: (1) baseline (*prior* to randomization and *Navegante* training) and (2) immediate post-intervention (6 months after the *Navegantes* in the intervention group are trained).

In-depth interviews. After post-intervention follow-up, we will conduct in-depth interviews with each *Navegante* in the intervention group (N=10) to explore and better understand their implementation of the intervention, their natural helping behaviors, and other lessons learned.

Aim 3:

The translation of findings into action is a CBPR hallmark,16,26,30,93-95,97,99,100,105,111,129,137,143,190-193 and we have developed an empowerment theory-based100,169,194,195 and highly collaborative process to do just that.95,100,166 We will organize and conduct a bilingual community forum to translate findings into practice, research, intervention, and policy priorities and recommendations.

Setting

The study will take place in community settings (e.g., community organizations) across NC.

Subjects selection criteria

• Inclusion Criteria

Aim 1:

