Sample size calculations are based on a follow-up adjusted baseline (or ANCOVA) model. We estimated the sample size needed (20 *Navegantes* and 160 social network members) by performing calculations in nQuery v8.7.

Interventions and Interactions

Aim 1:

Interviews will be digitally recorded. While interviews and focus groups can be conducted remotely via telephone and videoconferencing platforms (e.g., Zoom and WebEx), we will conduct them in-person if possible based on the current CDC recommendations. Safety precautions (e.g., personal protective equipment) will be followed as indicated. [name] and an infectious disease epidemiologist published guidelines for safely conducting community-based and community-engaged in-person research during COVID,151 which have been adopted by multiple Clinical and Translational Science Award hubs throughout the US and by CDC research teams.

The in-depth interview and focus groups guides. These guides will be structured to gather *descriptive* "deep"₁₅₂ qualitative data. An initial low-literacy assessment will collect demographic data. Guides will be developed iteratively with the steering committee and in consultation with the RADx-UP Coordination and Data Collection Center (CDCC) and consortium through ongoing literature review; brainstorming of domains and constructs; and drafting, review, and revision of potential questions. Because this Aim is

exploratory and designed to be **inductive**, the framework is subject to revision. This Aim's outcome will be a better understanding of the SEBI of COVID- 19 testing and vaccination among Spanish- speaking Latinx persons. Interview guides will adhere to best practices (e.g., creating non-leading/open-ended questions, ordering from general to specific, maintaining neutral tone, and depersonalizing behaviors by third-person-ing questions) to elicit knowledge, descriptions of experiences, opinions, and values.98.146.150.153-156

Aim 2:

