Evaluation of intervention impact. Data will be analyzed with an intent-to-treat approach.179 Randomization at the social network level will likely balance cluster-level baseline characteristics; however, as randomization may not precisely balance these, and there may be differences in social network member characteristics after network randomization, inverse probability weighting using propensity scores will be explored to balance baseline characteristics (both network and individual) between arms₁₈₀ using best practices.₁₈₁ Balance on propensity scores between intervention groups will be assessed using standardized differences.182 Propensity scores have been used in cluster RCTs.183 We will evaluate the intervention impact by comparing rates of past 6-month COVID-19 testing and vaccination completion (defined as complete dosage of approved vaccination: e.g., 2 Pfizer or Moderna doses or 1 Johnson & Johnson dose) between intervention and delayed-intervention group social network members at immediate post intervention (6 months after the intervention group *Navegantes* are trained), adjusting for baseline rates. This ANCOVA approach has the advantage of being unaffected by baseline differences; if baseline rates, by chance, were different, the intervention effect would be overestimated by looking at change scores and underestimated by a follow-up score analysis. The ANCOVA approach gives the same answer regardless of baseline imbalance. Additionally, the approach generally has greater statistical power to detect an intervention effect than the other methods. 184 Statistical analysis will be performed using generalized linear mixed modeling 185 for binary outcomes (sometimes termed randomeffects logistic regression). These models can assume a logit link for binary data (i.e., tested or vaccinated in past 6 months: yes/no) and allow for accounting for the within-group association of outcomes. If participants have repeated COVID-19 testing performed then an additional random effect for multiple testing will be considered, where appropriate. The generalized linear mixed model is an extension of general linear models that allows for non-independence of observations (e.g., within social networks).

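### No stratified, matched or constrained allocation is specified for the 20 networks, although baseline data are collected before they are randomized

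*Combined protocol and SAP*

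**What the plan says.** Objectives, Aim 2 gives eight members in each of 20 networks, "for a total of n=160 social network members", with ten Navegantes and "80 social network members per group". The order is explicit: "After baseline data collection, we will randomize" the Navegantes together with their networks. Methods and Measures, Design, Aim 2 repeats that the networks "will be randomly assigned to: intervention or delayed-intervention groups" and places the baseline assessment before randomization and training. Neither section names stratification, matching, minimization or covariate-constrained randomization, and no other section does.

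The Analytical Plan (Aim 2, evaluation of intervention impact) says "Randomization at the social network level will likely balance cluster-level baseline characteristics". The same sentence allows that balance may not be precise, and adds that "inverse probability weighting using propensity scores will be explored". The primary mixed logistic model contains the participant's own baseline yes/no value of the outcome, a treatment term and a random network effect. Other individual and network-level covariates may enter by backward elimination with a 10% change-in-estimate rule, with network-level covariates held to one or two. Propensity weighting appears again as a sensitivity analysis if many confounders are retained.

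**The concern.** What gets balanced here is networks, and there are only ten per arm. Because baseline testing and vaccination are known when the allocation is drawn, imbalance on them can be prevented at that moment at almost no cost. The plan instead deals with it afterwards. One part of that is pre-specified (the individual baseline term), one is exploratory (weighting) and one is chosen from the data (backward elimination).

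At stake are the credibility of a small trial whose arms may visibly differ at baseline, some precision, and the number of analytic choices made after the data are seen.

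**Working it through.** **Inputs from the documents.** 20 networks of 8: 20 × 8 = 160 members, and 10 × 8 = 80 per arm, which agrees with the stated size. The sample size section ("We estimated the sample size needed (20" Navegantes and 160 members) gives no alpha, power, rates, effect, ICC or dropout, so the size itself cannot be re-derived.

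**Assumptions.** Baseline prevalence p about 0.5, with other values shown. ICC 0.04, 0.07 and 0.14.

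**1. Gap between arms on one baseline outcome.** SD of the difference = √[2p(1−p)(1 + 7·ICC)/80].

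| ICC | 1 + 7·ICC | SD at p = 0.5 | P(gap > 10 points), p = 0.5 | p = 0.3 | p = 0.9 |
|---|---|---|---|---|---|
| 0.04 | 1.28 | 0.089 | 0.26 | 0.22 | 0.06 |
| 0.07 | 1.49 | 0.097 | 0.30 | 0.26 | 0.08 |
| 0.14 | 1.98 | 0.111 | 0.37 | 0.33 | 0.13 |

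These are normal approximations. Simulated simple 10:10 allocations at p = 0.5 give slightly less, 23% to 34%, because with 80 per arm a gap must reach 9/80 = 11.25 points to exceed 10. On at least one of two outcomes, taken as independent, simulation gives 41%, 46% and 56%.

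**2. Network-level characteristics.** For a continuous characteristic, the standardized difference has SD √(2/10) = 0.447. So P(|d| > 0.5) = 2[1 − Φ(0.5/0.447)] = 0.26. For at least one of k independent characteristics the probability is 1 − (1 − 0.264)^k: 0.46 for two, 0.60 for three, 0.71 for four. For a yes/no trait held by 8 of the 20 networks, the exact chance of a 5–3 split or worse is 0.65, and of 6–2 or worse 0.17.

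**3. Effect of restricting the allocation.** There are C(20,10) = 184,756 possible 10:10 splits, and the best-balanced 10% leave about 18,475. In simulation, choosing among these takes the chance of a baseline gap above 10 points, or above 0.5 SD on the characteristics scored, to about 0.

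**4. What the planned baseline term leaves behind.** The primary model uses each person's own yes/no value. The network's baseline rate carries further information about the network effect. In simulation (600 trials per cell, true conditional log odds ratio 1.0), each 10-point baseline gap still shifted the estimated log odds ratio after the planned adjustment. The shift was about 0.08 to 0.19 when network effects were stable over time, and 0.02 to 0.13 when they were correlated 0.8 over time.

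**5. Power, with the two changes separated.** Assumptions: network SD on the logit scale 0.42, 0.57 and 0.86 (ICC roughly 0.04, 0.07 and 0.14), individual SD 1, log odds ratio 0.9, quadrature fit, t reference on 18 or 17 df, 4,000 trials per cell.

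| ICC | Network effect | Plan | Simple allocation + network rate | Restricted + network rate |
|---|---|---|---|---|
| 0.04 | stable | 52.0% | 51.1% | 52.5% |
| 0.07 | stable | 50.3% | 50.4% | 51.4% |
| 0.14 | stable | 40.5% | 44.4% | 45.0% |
| 0.04 | 0.8 correlated | 51.0% | 50.7% | 51.8% |
| 0.07 | 0.8 correlated | 48.7% | 47.4% | 48.9% |
| 0.14 | 0.8 correlated | 40.0% | 41.4% | 42.5% |

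Restriction plus the network rate gains between 0.2 and 4.5 points over the plan. Treating the cells as independent, a difference has a Monte Carlo standard error of about √(2 × 0.25/4,000) = 1.1 points, so only the gains at ICC 0.14 stand clear of noise. A separate run of 1,600 trials per cell gave about 1 to 4 points, with the SD of the log odds ratio 1% to 6% lower. Runs under other settings with 600 or 1,300 trials per cell showed gains of 2 to 12 points, with standard errors of about 2 to 3 points on each difference. I do not rely on the upper end.

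Restriction without the network rate in the model lowered power by 0.7 to 1.9 points in all six cells above. In another simulation it gave a type I error of 3.2% to 3.5% at the larger ICCs with stable effects. Under the plan as written, and under the combined change, type I error stayed near 4% to 5%.

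**The case against.** The strongest reply is that the planned analysis is sound without any change. Randomization is unbiased on average, the mixed model's standard error reflects between-network variation, and the baseline outcome is already in the primary model. All of that stands. So does the point that most of the power gain at high ICC comes from the model term, which the plan's allowance of one or two network-level covariates already permits. Restriction itself adds only about 0.6 to 1.5 points.

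A reader might infer more than the documents support:

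- *That the sponsor chose unrestricted randomization.* The documents fix 10:10 and are silent on the procedure. Only the absence of a specified restriction can be asserted.
- *That a large imbalance is likely on any one outcome.* At 23% to 34% near 50% prevalence, and about 6% to 13% at 90%, it is not. It becomes likely only across several characteristics.
- *That the result would be biased or the test invalid.* Chance imbalance is random error in the realised trial. Simulated type I error is about 4% to 5%.
- *That imbalance is left to weighting alone.* The individual baseline term is pre-specified, and weighting is exploratory or a sensitivity analysis.
- *That restriction removes the case for all other adjustment.* Age, country of origin, employment and education are candidate covariates that the proposed score would not balance.

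The reply does not show that allocation should ignore data already in hand. The plan says that ANCOVA gives the same answer whatever the baseline imbalance. Step 4 shows that this does not hold fully when only the individual yes/no value is in the model.

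**Conclusion.** The point holds as a worthwhile improvement to a valid design. No restricted allocation is specified, and the expectation of balance is optimistic for ten networks per arm. The chance of a gap above 10 points on a given outcome is roughly one quarter to one third, assuming about 50% prevalence and ICC 0.04 to 0.14. It is smaller at extreme prevalence. A difference above 0.5 SD on at least one of three or more independent network characteristics has probability 0.60 or higher.

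The main gain is near-certain balance on the variables scored and less reliance on adjustment chosen after the data are seen. The power gain is small, about 1 to 4 points, and larger only if network effects are strong and stable. Prevalence, ICC and stability over time are assumptions, because the documents give none of them.

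**What to change.** 1. State the allocation procedure. Once baseline data are in for all 20 networks, draw one 10:10 split at random from the best-balanced 10%, scored on network baseline testing prevalence and network baseline vaccination prevalence. Define both as the outcomes are defined in the primary model.
2. Pre-specify the network baseline rate of the outcome as one of the one or two network-level covariates in the primary model, alongside the individual baseline value. Adopt this together with item 1, because restriction without it can be conservative.
3. Keep propensity weighting as a sensitivity analysis only.

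Cost: one allocation script and a short protocol and analysis-plan change, with no extra participants. Networks must be randomized together or in batches, and one network-level degree of freedom is used (18 to 17). If enrolment is staggered, two batches would work. With ten networks in each there are C(10,5) = 252 splits per batch, so the best 10% leaves about 25. Check beforehand that no two networks are then always, or never, placed together.

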Navegantes meet with providers and staff at COVID-19 testing and vaccination sites to provide feedback for multilevel changes to improve accessibility for Spanish-speaking Latinx communities.

Baseline and immediate post-intervention assessment. We will develop a Spanish-language assessment to collect data at baseline and immediate post-intervention (6 months post-baseline), based on Aim 1 findings, other relevant studies describing factors influencing COVID-19 testing and vaccination, our previous successes with peer navigation and mHealth strategies, and the theories underlying the intervention. **Table 2** outlines *draft* measurement priorities identified by our partnership while preparing this application. To ensure data harmonization, we will use the RADx-UP Common Data Elements and PhenX toolkit (https://www.phenxtoolkit.org/). The assessment, including final selection of measures,

Protocol version: Template updated 9.24.14 will be created using an *iterative* process by partners, including consultation with the RADx-UP CDCC and consortium

Table 2. Measurement priorities

Other variables

Outcome variables Primary: COVID-19 testing and vaccination including ever being tested, ever being vaccinated,

being up to date on recommended doses, and number of doses received

Demographic variables Age and date of birth; birthplace; ethnicity/race; language use; current living situation; zip code;

marital/partner status; family structure (e.g., children); educational attainment; current employment; financial status; immigration status; pregnancy status; insurance status

Symptoms COVID-19 symptoms and exposure to assess need for testing

Potentially mediating Awareness and knowledge about risk, testing, and prevention of COVID-19; intentions and variables readiness for COVID-19 testing and vaccination; perceived COVID-19 testing and vaccine a

readiness for COVID-19 testing and vaccination; perceived COVID-19 testing and vaccine access; knowledge of how to access testing and vaccination services; service use self-efficacy; perceived barriers to services; usual source of care; skills and self-efficacy to communicate effectively with providers; provider trust; history seeking and using prevention and care services; self-efficacy to overcome barriers; perceived provider discrimination; stigma related to COVID-19; social support; community attachment; perceived impact of positive test on job security; access to transportation

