The hypothesis that intervention and delayed-intervention groups differ in their prevalence, p, of COVID-19 testing or vaccination will be tested with the mixed-effects logistic model: Logit $(p_{ij}l) = \beta_0 + \beta_1 Y_{ijo} + \beta_2 INTVN + v_i$, where $p_{ij}l$ is the probability of testing or vaccination at immediate post-intervention for participant i in social network j, Y_{ij0} is 1 if participant i in social network j reports testing or vaccination at baseline and 0 otherwise, and, INTVN =1 for the intervention group and 0 for the delayed-intervention group. The random effect v_j is the random effect for participants in social network j. The variance component for this random effect addresses the within-social network correlation. Under this model, β_2

corresponds to the difference in prevalence of testing or vaccination at immediate post-intervention between the intervention and delayed-intervention groups on the logit scale. This random-effects logistic regression model will be fit using adaptive Gaussian quadrature in SAS PROC GLIMMIX.186

This regression approach will allow us to produce estimates of prevalence and prevalence change additionally *adjusting for individual and cluster-level covariates*, which will be compared to unadjusted estimates. Individual-level covariates may include age, country of origin, employment status, and education level. Because there are only a small number of clusters (social networks), the literature advises that the number of cluster-level covariates should be limited to one or two key variables. 187, 188 To assess the importance of covariates, we will use a backwards elimination model building approach, with primary consideration on assessment of confounding on the intervention-group difference. If confounding is present (defined to be greater than a 10% change in the regression estimate of the intervention-group effect), the confounder will be retained in the multivariable model. If many confounders are retained, alternative/sensitivity analyses will be conducted using propensity score weighting. All analyses will be 2-sided. 189 Note: While a better understanding of the relationships between members of social networks can be interesting, social network analysis is beyond the scope of this proposal based on our hypotheses and analysis plans.

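### The test model adjusts only for past behaviour; pre-declaring the planned baseline intention/readiness score as a fixed term would add power, though not a narrower interval

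*Combined protocol and SAP*

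**What the plan says.** **Test model** (Analytical Plan, Aim 2, evaluation of intervention impact). The hypothesis is tested with a random-intercept logistic model holding Y_ij0, arm and a network effect. Y_ij0 "is 1 if participant i in social network j reports testing or vaccination at baseline and 0 otherwise". The same section defines vaccination completion as a complete dose series. It defends baseline adjustment partly because "the approach generally has greater statistical power to detect an intervention effect than the other methods".

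**Further covariates** (same section). These belong to additional adjusted models that are compared with unadjusted estimates: "Individual-level covariates may include age, country of origin, employment status, and education level". Selection is by backward elimination, and a covariate counts as a confounder to be kept on a criterion "defined to be greater than a 10% change in the regression estimate of the intervention-group effect". The cap of one or two covariates applies to network-level variables only. Propensity-score weighting on baseline characteristics is to be explored, with no variables named.

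**Intention and readiness** (Interventions and Interactions, Aim 2, Table 2). The potential mediators include intentions and "readiness for COVID-19 testing and vaccination; perceived COVID-19 testing and vaccine access". The assessment is given at baseline and at 6 months, and the Design section places baseline before randomization. The table is labelled draft: "measurement priorities identified by our partnership while preparing this application". Final selection of measures is still to come.

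**Sample size** (Sample Size, Aim 2). 20 Navegantes and 160 members, said to rest on a baseline-adjusted model. No rates, effect, ICC, alpha, power or baseline correlation are given.

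**The concern.** The plan relies on baseline adjustment for power, yet the only adjuster in the test is past behaviour. For vaccination that adjuster may do little. If Y_ij0 is coded as series completion, as the outcome is, every member who can still complete vaccination has Y_ij0 = 0. The covariate is then constant among the people the intervention can move. Members are not screened on vaccination status, so the size of that group is unknown.

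A baseline intention or readiness score can vary within that group. It is fixed before randomization, so it cannot be affected by arm, and its listing as a potential mediator does not bar using the baseline value as a covariate. As written, no analysis names it as one. With only 10 networks per arm, a few points of power are worth having when they need no new data. Left to the additional models, use of the score would depend on a change-in-estimate rule applied to the trial's own data.

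**Working it through.** **1. The plan's own figure.** The 20 networks and 160 members cannot be reproduced, because no numerical input is stated. Everything below is therefore a range under assumptions.

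**2. Approximate calculation.** Assumed: alpha 0.05 two-sided, 30% versus 50%, ICC 0.05, and a score that explains a further fraction R2 of the variance.

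- Design effect = 1 + 7 × 0.05 = 1.35.
- Effective members per arm = 80 / 1.35 = 59.3. With R2 = 0.20, 59.3 / 0.80 = 74.1.
- z = [0.20 − 1.96 √(2 × 0.4 × 0.6 / n)] / √((0.21 + 0.25) / n).
- n = 59.3 gives z = 0.27 and power 60.6%. n = 74.1 gives z = 0.54 and power 70.4%.

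| ICC | R2 = 0 | 0.10 | 0.20 | 0.30 |
|---|---|---|---|---|
| 0.01 | 70.8% | 75.4% | 80.2% | 85.2% |
| 0.05 | 60.6% | 65.2% | 70.4% | 76.1% |
| 0.10 | 50.8% | 55.2% | 60.2% | 66.1% |

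This is a linear approximation. The plan's model is logistic, so step 3 is the better guide.

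**3. Simulation of the plan's model with Y_ij0 kept.** 20 networks of 8, 500 runs per row, t test on 18 df. Assumed: network SD 0.42 on the logit scale (0.176 / (0.176 + 3.290) = ICC 0.05), log-odds 1.0 for Y_ij0, and true conditional intervention log odds ratio 1.0. Each data set is fitted without and then with a standardised baseline score.

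| Log-odds per SD of score | Power | Estimate of beta_2 | Median SE | Estimate moves >10% |
|---|---|---|---|---|
| 0 | 69.2 → 69.0% | 1.02 → 1.03 | 0.374 → 0.378 | 4% of runs |
| 0.5 | 62.6 → 64.2% | 0.96 → 1.01 | 0.367 → 0.383 | 36% |
| 1.0 | 53.8 → 61.4% | 0.83 → 1.00 | 0.363 → 0.407 | 76% |
| 1.0, score strongly tied to past behaviour | 58.8 → 63.4% | 0.92 → 1.05 | 0.385 → 0.420 | 67% |
| 1.5 | 45.0 → 57.2% | 0.73 → 1.04 | 0.358 → 0.444 | 89% |

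Monte Carlo error is about 2 points per power figure; paired differences are tighter. With no true effect (log-odds 1.0), rejection is 5.0 → 5.2%.

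A separate set of the same design (500 runs per cell) gave gains of about 1 point at 0 to 0.4 per SD, 5–6 at 0.7 and 7–12 at 1.1. The SE rose from 0.39 to 0.43 at 1.1.

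**4. Members not yet vaccinated.** Four per network, 20% versus 48%, ICC 0.05, 1,300 runs per cell; here completion-coded Y_ij0 is constant and drops out. For odds ratios per SD of 1.5, 2 and 3, power goes 66 → 69%, 66 → 69% and 64 → 72%. In null runs (400 per setting, odds ratio 2 per SD), rejection was 1.5–2.5% without the score and 2.3–3.0% with it.

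**5. Power, not precision.** At 1.0 per SD the ratio of estimate to SE moves from 0.833 / 0.363 = 2.29 to 1.005 / 0.407 = 2.47, against a critical value of 2.10. The 95% half-width goes from 2.10 × 0.363 = 0.76 to 2.10 × 0.407 = 0.85. The estimate grows by 21% and the SE by 12%. The test is stronger, the interval on the logit scale is wider, and beta_2 now estimates an effect conditional on intention.

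**6. The 10% rule.** Even with randomized arms, a prognostic score often moves the conditional log odds ratio by more than 10% (last column of step 3). The rule therefore does not separate confounding from prognostic value, and it makes inclusion depend on the data.

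**The case against.** The strongest case against is that this is an efficiency preference and not an error. Much of it limits the point.

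- **Precision.** A reader might infer that the trial gives up precision. On the plan's logit scale that is wrong: the SE of beta_2 rises when the score is added. Only power is gained.
- **An empty Y_ij0.** A reader might infer that past behaviour carries no information for vaccination. The plan codes Y_ij0 as reported testing or vaccination and does not say completion. A member with one of two doses may be coded 1 and can still complete. Being up to date and number of doses are also listed as primary outcomes, and neither is once-only. The argument holds only under completion coding.
- **Data in hand.** A reader might infer that the scores are already secured. Table 2 is a draft, and no instrument or separate testing and vaccination scales are defined.
- **Exclusion.** A reader might infer that the plan rules these scores out. The covariate list is open, and the exploratory weighting could include them. They are unnamed, not barred. Neither route, however, puts them in the test.
- **Size.** No document gives the prognostic strength of intention, and nothing singles it out over perceived access or barriers, which Table 2 also lists. Overlap with past behaviour cuts the gain from 7.6 to 4.6 points in step 3. In step 4, null rejection was slightly higher with the score, so part of a small gain there may come from a less conservative test.

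What survives is that the test model has one baseline term, a planned pre-randomization predictor is named only as a mediator, and adding it costs almost nothing even if it proves useless (69.2% versus 69.0%).

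**Conclusion.** The point holds as a low-cost improvement to the test model. The model adjusts only for past behaviour, while baseline intention and readiness are planned but not named as covariates in any analysis. Pre-declaring a score would add about 0 to 3 points of power if it is a weak predictor and about 5 to 12 if moderate to strong. One cell falls below that pattern: four unvaccinated members per network at an odds ratio of 2 per SD gave 3 points. Null rejection stayed near or below 5% with and without the score.

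These figures rest on assumed event rates, ICC, effect size and, above all, prognostic strength. They do not show that the planned sample is inadequate or that the planned test is invalid. The argument specific to vaccination also depends on Y_ij0 being coded as series completion, which the plan leaves open.

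**What to change.** In the Aim 2 model specification, provided the items are kept in the final assessment:

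- Add one fixed, pre-declared term per behaviour, testing intention/readiness in the testing model and vaccination intention/readiness in the vaccination model: logit(p) = β0 + β1 Y_ij0 + β2 INTVN + β3 Score_ij0 + v_j.
- Exempt this term from backward elimination and the 10% rule.
- Use only the pre-randomization value; leave follow-up values as mediators.
- Define the score (items, scoring, handling of missing items) before randomization, and state how Y_ij0 is coded for vaccination.
- State that the expected benefit is power and not a narrower interval for β2, that β2 becomes conditional on intention, and what prognostic strength is assumed. Report adjusted prevalences by arm beside β2.

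Cost: a short SAP edit, one member-level degree of freedom, and the work of defining the score in advance. No data collection is added beyond what Table 2 plans.
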